13.5 Secondary Objectives

The percentage of patients with unacceptable adverse events that are possibly, probably, or definitely related to perampanel treatment will be calculated. Unacceptable adverse events include all CTCAE Grade 4 or 5 toxicities that are possibly, probably, or definitely related to perampanel, as well as suicidal ideation (any grade) or suicide attempt (Grade 3-5).

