5.2.2 Clinical experience

Perampanel is currently FDA-approved for the adjunctive treatment of refractory partial seizures in patient \geq 12 years of age. In a pooled analysis of three phase III studies involving 1,478 patients, median change in partial seizure frequency was greater with perampanel in comparison to placebo.² Specifically, median change in partial seizure frequencies was as follows: perampanel 4 mg, -23.3%; perampanel 8 mg, -28.8%; perampanel 12 mg, -27.2%; and placebo, -12.8%. Moreover, 50% responder rates were as follows: perampanel 4 mg, 28.5%; perampanel 8 mg, 35.3%; perampanel 12 mg, 35.0%; and placebo, 19.0%. In this pooled analysis, perampanel was well tolerated with the most frequent treatment-emergent adverse events (TEAEs) being dizziness, somnolence, and headache. Of note, there were no deaths reported and no clinically meaningful mean change in laboratory values, electrocardiography (ECG) findings, or vital signs.¹⁰ TEAEs from the pooled analysis are listed in the table below for perampanel dose 2 mg to 12 mg and placebo.

Adverse Event, n (%)	Placebo (n=442)	Perampanel 2 mg (n=180)	Perampanel 4 mg (n=172)	Perampanel 8 mg (n=431)	Perampanel 12 mg (n=255)
Any TEAE	294 (66.5)	111 (61.7)	111 (64.5)	350 (81.2)	227 (89.0)
Dizziness	40 (9.0)	18 (10.0)	28 (16.3)	137 (31.8)	109 (42.7)
Somnolence	32 (7.2)	22 (12.2)	16 (9.3)	67 (15.5)	45 (17.6)
Headache	50 (11.3)	16 (8.9)	19 (11.0)	49 (11.4)	34 (13.3)
Fatigue	21 (4.8)	8 (4.4)	13 (7.6)	36 (8.4)	31 (12.2)
Irritability	13 (2.9)	7 (3.9)	7 (4.1)	29 (6.7)	30 (11.8)
Nausea	20 (4.5)	4 (2.2)	5 (2.9)	25 (5.8)	20 (7.8)
Fall	15 (3.4)	2 (1.1)	3 (1.7)	22 (5.1)	26 (10.2)
Nasopharyngitis	18 (4.1)	7 (3.9)	9 (5.2)	23 (5.3)	11 (4.3)
Upper respiratory	12 (2.7)	11 (6.1)	6 (3.5)	14 (3.2)	10 (3.9)

tract infection					
Ataxia	0 (0.0)	0 (0.0)	1 (0.6)	14 (3.2)	21 (8.2)
Balance disorder	2 (0.5)	0 (0.0)	0 (0.0)	22 (5.1)	8 (3.1)

Most TEAEs were mild to moderate and appeared to be dose related. From the pooled analyses, discontinuation of perampanel at 4 mg was 2.9%, at 8 mg was 7.7%, and at 12 mg was 19.2% in comparison to placebo.¹⁰ Common discontinuation TEAEs were dizziness, convulsion, and somnolence.

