6 OBJECTIVES AND ENDPOINTS

	Objective	Endpoint	Analysis
Primary	To determine the efficacy of perampanel as an adjunctive AED in patients with primary glioma presenting refractory partial onset seizure activity	Percentage of patients with ≥50% seizure reduction during the treatment period compared with seizure frequency before initiation of perampanel (i.e. 50% responder rate)	See Section 13.4
Secondary	To assess the safety and tolerability of perampanel as an adjunctive AED in patients with primary glioma presenting with refractory partial onset seizure activity	The percentage of patients who experience a adverse event possibly, probably, or definitely attributable to perampanel treatment	See Section 13.5
Exploratory	To evaluate the effect that perampanel has on neurocognition and patient-reported outcomes of quality of life (QoL) in patients with primary glioma presenting with refractory partial onset seizure activity	Mean change from baseline for each neurocognitive and QoL subscale score at each follow-up assessment	See Section 13.6

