11.1 Adverse Events

An adverse event (AE) is any untoward medical occurrence in a subject receiving study drug and which does not necessarily have a causal relationship with this treatment. For this protocol, the definition of AE also includes worsening of any pre-existing medical condition. An AE can therefore be any unfavorable and unintended or worsening sign (including an abnormal laboratory finding), symptom, or disease temporally associated with the use of perampanel, whether or not related to use of the perampanel. Abnormal

laboratory findings without clinical significance (based on the PI's judgment) should not be recorded as AEs. But laboratory value changes that require therapy or adjustment in prior therapy are considered adverse events.

From the time the subject starts the first dose of perampanel through the End of Study visit (as defined in Section 10.6), all AEs must be recorded in the subject medical record and adverse events case report form.

AEs will be assessed according to the CTCAE version 4.0. If CTCAE grading does not exist for an AE, the severity of the AE will be graded as mild (1), moderate (2), severe (3), life-threatening (4), or fatal (5).

Attribution of AEs will be indicated as follows:

- Definite: The AE is clearly related to the study drug
- Probably: The AE is likely related to the study drug
- Possible: The AE may be related to the study drug
- Unlikely: The AE is doubtfully related to the study drug
- Unrelated: The AE is clearly NOT related to the study drug

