12 QUALITY CONTROL AND QUALITY ASSURANCE

12.1 Monitoring

This clinical research study will be monitored both internally by the PI and institutionally by the Duke Cancer Institute (DCI). In terms of internal review the PI will continuously monitor and tabulate adverse events. Appropriate reporting to the Duke University Medical Center IRB will be made. If an unexpected frequency of Grade III or IV events occur, depending on their nature, action appropriate to the nature and frequency of these adverse events will be taken. This may require a protocol amendment, dose de-escalation, or

potentially closure of the study. The PI of this study will also continuously monitor the conduct, data, and safety of this study to ensure that:

- Interim analyses occur as scheduled;
- Stopping rules for toxicity and/or response are met;
- Risk/benefit ratio is not altered to the detriment of the subjects;
- Appropriate internal monitoring of AEs and outcomes is done;
- Over-accrual does not occur;
- Under-accrual is addressed with appropriate amendments or actions;
- Data are being appropriately collected in a reasonably timely manner.

DCI review and monitoring of this protocol occurs in accordance with the NCI-approved Data and Safety Monitoring Plan. Briefly, protocol review begins with an initial review by the Cancer Protocol Committee (CPC), which assesses the ethics and safety of the protocol. Documentation of these assessments will be maintained. Formal, independent monitoring will be conducted by the DCI Monitoring Team after the first 3 subjects are enrolled, followed by annual monitoring of 1-3 subjects until the study is closed to enrollment and subjects are no longer receiving study interventions that are more than minimal risk. DCI Monitoring Team reports and additional data/safety/toxicity reports submitted by the PI will be reviewed by the Safety Oversight Committee (SOC) on an annual basis. Additional monitoring may be prompted by findings from monitoring visits, unexpected frequency of serious and/or unexpected toxicities, or other concerns. Monitoring visits may also be initiated upon request by DUHS and DCI Leadership, CPC, SOC, a sponsor, an investigator, or the IRB.

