13.3 Treatments

The total number of days that the patient received perampanel treatment will be determined for each patient. The percentage of patients who had dose modifications not consistent with the planned dosing during titration, treatment, and tapering will be tabulated by dosing period (i.e. titration, treatment, and tapering).

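### The secondary safety endpoint in Section 6 (any attributable adverse event) is not the one Section 13.5 calculates (attributable Grade 4-5 events plus suicidality), and no statistical section specifies the former

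*Combined protocol and SAP*

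**What the plan says.** The table in Section 6 (Objectives and Endpoints) pairs the safety and tolerability objective with a single endpoint: "The percentage of patients who experience a adverse event possibly, probably, or definitely attributable to perampanel treatment". There is no threshold for grade or seriousness. The analysis column reads "See Section 13.5".

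Section 13.5 then states: "The percentage of patients with unacceptable adverse events that are possibly, probably, or definitely related to perampanel treatment will be calculated". It goes on to define the term: "Unacceptable adverse events include all CTCAE Grade 4 or 5 toxicities that are possibly, probably, or definitely related to perampanel". To these it adds suicidal ideation of any grade and suicide attempts graded 3 to 5.

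Three other places bear on the point:

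- Section 11.1 requires that "all AEs must be recorded in the subject medical record and adverse events case report form", and sets out CTCAE grading and a five-level attribution scale.
- Section 13.3 covers days on drug, and says that the percentage of patients with "dose modifications not consistent with the planned dosing during titration, treatment, and tapering will be tabulated by dosing period".
- Section 12.1 says that "the PI will continuously monitor and tabulate adverse events", as part of internal monitoring.

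**The concern.** One cross-reference joins two different variables. A patient with attributable Grade 2 dizziness or Grade 3 aggression is a case under Section 6 and not under Section 13.5. If the analysis follows Section 13.5, the trial's only declared secondary endpoint goes unreported and a narrower quantity takes its place.

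This matters because the objective covers tolerability as well as severe toxicity. Section 5.2.2 says of the pooled phase III data: "Most TEAEs were mild to moderate and appeared to be dose related". The events most likely to occur thus lie mainly in the grades that Section 13.5 leaves out. The boxed warning reproduced in Section 3.4 lists aggression, hostility, irritability, anger and homicidal ideation. Among psychiatric events, Section 13.5 singles out only suicidality for inclusion below Grade 4.

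There are two practical risks. A reader who knows the Section 6 endpoint could take the Section 13.5 percentage for the attributable-event rate. And with two definitions in force, the choice between them could be made after the data are seen.

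**Working it through.** **Step 1: the two definitions side by side.** A patient counts if at least one event meets the condition.

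| Event | Section 6 | Section 13.5 |
|---|---|---|
| Attributable, Grade 1-3, not suicidality | counts | does not count |
| Attributable, Grade 4-5 | counts | counts |
| Attributable suicidal ideation, any grade | counts | counts |
| Attributable suicide attempt, Grade 3-5 | counts | counts |
| Suicidality judged unrelated | does not count | unclear (see below) |

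On the last row, the first sentence of Section 13.5 limits unacceptable events to related ones. The second sentence lists the suicidality items without repeating that condition. The natural reading is that relatedness applies throughout, but the text should say so.

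**Step 2: does another section specify the Section 6 percentage?**

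- Sections 3.5 and 13.8 deal only with the responder rate.
- Section 13.1 names the safety population (all who receive perampanel) but no variable.
- Section 13.2 covers baseline characteristics.
- Section 13.3 covers exposure and dose modification, which is indirect evidence on tolerability.
- Section 13.4, including its additional secondary analysis, concerns seizure frequency.
- Section 13.6 covers neurocognition and quality of life, and Section 13.7 states that there is no interim analysis.
- Section 12.1 describes monitoring, not an endpoint analysis.

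None specifies the percentage of patients with any attributable event.

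**Step 3: what the documents show about event frequency.** From the table in Section 5.2.2, 8 mg (n=431) against placebo (n=442), all causes:

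| Event | 8 mg | Placebo | Difference (points) |
|---|---|---|---|
| Any TEAE | 350/431 = 81.2% | 294/442 = 66.5% | 14.7 |
| Dizziness | 137/431 = 31.8% | 40/442 = 9.0% | 22.7 |
| Somnolence | 67/431 = 15.5% | 32/442 = 7.2% | 8.3 |
| Irritability | 29/431 = 6.7% | 13/442 = 2.9% | 3.8 |
| Fall | 22/431 = 5.1% | 15/442 = 3.4% | 1.7 |

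Differences are taken before rounding. These rates are neither attributed nor graded, so they show that events are common but do not measure the gap between the two definitions.

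**Step 4: an illustrative range.** The documents give no attributable rate and no Grade 4-5 rate, so both are assumed. The denominator is the planned enrolment of 71, taking all as treated. Intervals are exact (Clopper-Pearson) 95%.

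| Assumed quantity | Low | High |
|---|---|---|
| Any-grade attributable (Section 6) | 11/71 = 15.5% (8.0 to 26.0) | 57/71 = 80.3% (69.1 to 88.8) |
| Unacceptable (Section 13.5) | 0/71 = 0% (0 to 5.1) | 7/71 = 9.9% (4.1 to 19.3) |

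For orientation only, the Section 6 limits lie near the pooled excess over placebo (0.147 × 71 = 10.4 patients) and the pooled all-cause rate (0.812 × 71 = 57.7 patients).

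- Smallest gap: 15.5 − 9.9 = 5.6 points.
- Largest gap: 80.3 − 0 = 80.3 points.

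**The case against.** The best defence is that this is a single combined document, so Section 6 binds as much as Section 13.5. Everything needed for the Section 6 percentage is present: the numerator in Section 6, the denominator in Sections 7.4 and 13.1, and grading and attribution in Section 11.1. A simple percentage needs no model or test, and a team that followed Section 6 could report it. Section 13.5 also labels its own figure as unacceptable events and defines the term, which limits confusion.

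Part of this stands. The figure can be recovered at reporting, nothing in the primary test or sample size is affected, and no stopping rule depends on it. But it does not remove the contradiction. Section 6 hands the analysis to Section 13.5, and Section 13.5 names a different variable. That the right percentage could be computed does not mean the plan says it will be.

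A second objection is that a range of 6 to 80 points says little, because it rests on assumed rates and on pooled figures that are all-cause and come from trials with a placebo arm, which this trial lacks. That is fair. The range only illustrates; the finding rests on the text, and its direction on the statement that most events were mild to moderate.

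A third is that the mismatch could equally be closed by narrowing Section 6. That would restore consistency, but it would leave a tolerability objective measured almost wholly by Grade 4-5 toxicity.

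**Conclusion.** The concern holds. The declared secondary endpoint and the planned analysis are different quantities, and no statistical section specifies the declared one. This follows from the wording alone and needs no assumption about event rates. The one reading involved is that relatedness applies to the suicidality items, which makes the Section 13.5 variable a subset of the Section 6 endpoint.

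The numerical size is unknown. It was bracketed in the working only under assumed rates and with all 71 enrolled patients treated. The consequence is moderate: the figure is descriptive, but it is the trial's only secondary endpoint, so it should be corrected before analysis.

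**What to change.** Make Sections 6 and 13.5 agree. The preferred wording for Section 13.5 would specify:

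1. In all patients who receive perampanel, the percentage with at least one adverse event possibly, probably or definitely attributable to it.
2. The same percentage by maximum grade: any grade, Grade 3 or higher, and Grade 4-5, each with an exact confidence interval.
3. Unacceptable events as a separately named subset, stating whether suicidality must be judged related in order to count.

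The first item alone closes the contradiction. The grade breakdown and intervals make the result more useful at little cost.

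Two rows are optional: attributable psychiatric and behavioural events, from the same data; and discontinuation due to adverse events, if the reason is captured.

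The main change costs a text correction and the programming of one table, because Section 11.1 already requires every adverse event to be recorded, with severity grading and attribution. The discontinuation row may need an added data field, since Section 10.7 lists possible reasons for withdrawal but does not say that the reason is recorded.

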7.1.2 Concomitant Medications

With concomitant use, perampanel, at a dose of 12 mg/day, reduced levonorgestrel exposure by approximately 40%. Use of perampanel with oral or implant contraceptives containing levonorgestrel may render them less effective. Therefore, additional non-hormonal forms of contraception are recommended (please see the FYCOMPA FDA-approved labeling dated 2/12/2014).¹

The concomitant use of known CYP enzyme inducers including carbamazepine, phenytoin, or oxcarbazepine with perampanel decreased the plasma levels of perampanel by approximately 50~67%. The starting doses for perampanel should be increased in the presence of enzyme-inducing AEDs.¹ When these enzyme-inducing AEDs are introduced or withdrawn from a patient's treatment regimen, patient should be closely monitored for clinical response and tolerability. As noted, however, the decrease in the therapeutic effect seen in patients on concomitant treatment, was not affected by use of higher doses (8 mg to 12 mg).¹

Concomitant use of perampanel with other strong CYP3A inducers (e.g., rifampin, St. John's wort) should be avoided.¹

The concomitant use of perampanel and CNS depressants including alcohol may increase CNS depression.¹ A pharmacodynamic interaction study in healthy subjects found that the effects of perampanel on complex tasks such as driving ability were additive or supra-additive to the impairment effects of alcohol. Multiple dosing of perampanel 12 mg/day also enhanced the effects of alcohol to interfere with vigilance and alertness, and increased levels of anger, confusion, and depression. These effects may also be seen when perampanel is used in combination with other CNS depressants. Care should be taken when administering perampanel with these agents. Patients should limit activity until they have experience with concomitant use of CNS depressants (e.g. benzodiazepines, narcotics, barbiturates, sedating antihistamines). Advise patients not to drive or operate machinery until they have gained sufficient experience on perampanel to gauge whether it adversely affects these activities.¹

Perampanel is FDA-approved as adjunctive therapy for refractory partial onset seizures, so it will be utilized in concert with other AEDs.

If subjects are receiving chemotherapy during the study, these medications, the doses, and any associated serious adverse events will be recorded.

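### Sections 6 and 13.5 define two different safety endpoints, both filtered by investigator attribution, and Section 13 plans no all-cause adverse-event summary

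*Combined protocol and SAP*

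**What the plan says.** The secondary objective covers both safety and tolerability (Sections 3.1 and 6). Two places define how it is measured.

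- Section 6 gives the endpoint as: "The percentage of patients who experience a adverse event possibly, probably, or definitely attributable to perampanel treatment". It sets no grade limit and refers to Section 13.5 for the analysis.
- Section 13.5 says: "The percentage of patients with unacceptable adverse events that are possibly, probably, or definitely related to perampanel treatment will be calculated". It continues: "Unacceptable adverse events include all CTCAE Grade 4 or 5 toxicities that are possibly, probably, or definitely related to perampanel", and adds "as well as suicidal ideation (any grade) or suicide attempt (Grade 3-5".

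Collection is broader than analysis. Section 11.1 defines an adverse event as one "temporally associated with the use of perampanel, whether or not related to use of the perampanel", grades it by CTCAE version 4.0, codes attribution on five levels from definite to unrelated, and requires that "all AEs must be recorded in the subject medical record and adverse events case report form". Sections 7.4 and 13.1 put all treated patients in the safety set; planned enrolment is 71.

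The trial has one arm, with blinding and randomization marked not applicable (7.1.3, 7.1.4). Patients on active chemotherapy may enrol (7.1). Under Section 11 the principal investigator identifies, documents and signs off adverse events. No independent adjudication of causality is described.

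**The concern.** Dizziness, somnolence, fatigue, ataxia and irritability are listed as perampanel reactions in Sections 3.4 and 5.2.2. Glioma and its treatment can plausibly produce the same symptoms. With no control arm, nothing in the trial can check whether a given episode was rightly attributed. An endpoint counting only attributable events therefore mixes how often events occur with how the investigator assigns cause.

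The two definitions can also give very different percentages from the same data. One counts a patient with any possibly related Grade 1 event; the other ignores related events below Grade 4 unless they are suicidality. If this is not settled beforehand, the choice could be made after the data are seen.

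At stake is a usable description of how patients with glioma tolerate the drug. The primary efficacy test is unaffected.

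**Working it through.** **1. The two endpoints side by side**

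| | Section 6 | Section 13.5 |
|---|---|---|
| Attribution | possible, probable or definite | possible, probable or definite |
| Grade | any | 4 or 5, plus suicidality |
| By event term | no | no |
| Regardless of cause | no | no, unless suicidality is read that way |

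Neither gives a rate per term. Events coded unlikely or unrelated drop out of both. Related Grade 1 to 3 events other than suicidality drop out of 13.5. Section 12.1 has the investigator act on an unexpected frequency of Grade III or IV events, so Grade 3 is watched in monitoring but is absent from the planned report.

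**2. Suicidality.** The first sentence of 13.5 limits the percentage to related events. The second attaches attribution to Grade 4 or 5 toxicities and then lists suicidal ideation and attempt with no attribution condition of their own. Both readings are possible.

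**3. The reference table in Section 5.2.2.** Its percentages for any event reproduce from the counts:

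- 8 mg: 350/431 = 81.2%
- placebo: 294/442 = 66.5%
- difference: 81.2 − 66.5 = 14.7 points

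The table has no attribution or grade column. It labels its events treatment-emergent; that they are of any cause is an inference, though a fair one with 66.5% on placebo. A related-only percentage is therefore a different quantity. For 13.5 the Grade 4 or 5 limit alone already prevents comparison.

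**4. Illustration for the Section 6 endpoint.** Let m be the share of patients with an event whose events are all attributed elsewhere. The documents give no value, so m is assumed, with a range of 0 to 50%.

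Reported rate = true rate × (1 − m). With a true rate of 81.2%:

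- m = 0: 81.2%
- m = 10%: 81.2 × 0.90 = 73.1%
- m = 25%: 81.2 × 0.75 = 60.9%
- m = 50%: 81.2 × 0.50 = 40.6%

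The placebo level is reached at m = 1 − 66.5/81.2 = 0.18.

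In the same patients a related-only rate can never exceed the all-cause rate. As a measure of harm caused by the drug, however, it can err either way: if every event were coded possible, 81.2% would be reported, although the table's excess over placebo is 14.7 points.

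**5. What an all-cause table would give.** No sample size or target is stated for safety. With 71 treated patients and the 8 mg rates, exact (Clopper-Pearson) 95% intervals are:

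- any event: 0.812 × 71 ≈ 58; 58/71 gives 70.7 to 89.9%
- dizziness: 0.318 × 71 ≈ 23; 23/71 gives 21.8 to 44.5%

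By contrast, a 13.5 result of 0/71 would have a two-sided 95% upper limit of 1 − 0.025^(1/71) = 5.1%, and would say nothing about lower grades.

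**The case against.** The strongest reply is that the data are complete and the filter is wide. Section 11.1 requires all events to be recorded, and possible means only that the drug may be involved. An open-label investigator who knows the listed reactions could over-attribute as easily as under-attribute. Section 13.5 is descriptive, with no safety benchmark, and no formal comparison with Section 5.2.2 is planned. This stands: neither the direction nor the size of bias can be claimed. It does not supply the missing summary.

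A reader might infer several stronger points that the documents do not support:

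- **That chemotherapy-related events go unrecorded.** Section 7.1.2 says of patients on chemotherapy that "any associated serious adverse events will be recorded". It does not say that only serious events are recorded. It belongs to a concomitant-medication paragraph, and Section 11.1 covers all events.
- **That the trial would report a falsely low dizziness rate.** No rate for dizziness or any other single term is planned in either section.
- **That suicidality is certainly filtered by attribution.** The wording is ambiguous, as shown above.
- **That no other safety information exists, or that the objective cannot be answered.** Section 12.1 has the investigator tabulate adverse events for monitoring, Section 13.3 tabulates unplanned dose modifications by period, and Section 13.6 reports quality-of-life and neurocognitive change. None of these is filtered by attribution. They supplement an adverse-event summary but do not replace one.

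**Conclusion.** The point holds as a gap in the planned analysis. Sections 6 and 13.5 must be reconciled. Both rest on unblinded attribution in a single-arm trial with competing causes, and Section 13 contains no all-cause adverse-event summary. Tolerability is described poorly because related events below Grade 4 are missing from 13.5, suicidality apart, and neither percentage can be read beside the Section 5.2.2 table.

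The possible size is shown only by illustration: an 18% share attributed elsewhere would bring 81.2% down to about 66.5%. This rests on an assumed m and on borrowing the 8 mg rate from a general epilepsy population. This is a change that should be made.

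**What to change.** - **Section 13.5, main table.** Report the percentage of treated patients with each treatment-emergent CTCAE term, by worst grade and regardless of attribution, with exact 95% intervals. Give the percentage attributable to perampanel beside it.
- **Section 13.5, suicidality.** State that suicidal ideation and suicide attempt count regardless of attribution.
- **Sections 6 and 13.5.** State one secondary safety endpoint in both. If any attributable event and unacceptable events are both wanted, name both in each section and say which is the main one.
- **Section 7.1.2, optional.** Refer to Section 11.1 for adverse-event recording in patients on chemotherapy. This aligns wording and does not correct an error.

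The cost is one extra table from data that Section 11.1 already requires; no new visits, data items or patients are needed. The downside is that all-cause rates will include tumour and chemotherapy events. Even with the fix, comparison with Section 5.2.2 will not be clean, and the report should say so.

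### The tolerability part of the only secondary objective has no endpoint for stopping perampanel because of an adverse event, and the Section 13.5 statistic is narrower than the Section 6 endpoint

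*Combined protocol and SAP*

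**What the plan says.** Section 6 of the combined protocol and SAP gives one secondary objective: "To assess the safety and tolerability of perampanel as an adjunctive AED in patients with primary glioma presenting with refractory partial onset seizure activity". Its endpoint is "The percentage of patients who experience a adverse event possibly, probably, or definitely attributable to perampanel treatment", with no limit on grade. For the analysis, Section 6 points to Section 13.5.

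Section 13.5 plans something narrower: "The percentage of patients with unacceptable adverse events that are possibly, probably, or definitely related to perampanel treatment will be calculated". It then defines the term: "Unacceptable adverse events include all CTCAE Grade 4 or 5 toxicities that are possibly, probably, or definitely related to perampanel", to which it adds suicidal ideation of any grade and suicide attempt of Grade 3 to 5. Nothing else is planned for this objective.

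Dosing is summarised separately, in Section 13.3. There "The total number of days that the patient received perampanel treatment will be determined for each patient", and a second summary is "The percentage of patients who had dose modifications not consistent with the planned dosing during titration, treatment, and tapering", shown by dosing period. No reason for a modification is asked for.

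Section 13.1 puts all treated patients in the safety analyses but only those who finish the treatment period in the efficacy analyses; Section 7.4 agrees. Section 7.1 lets the physician change the dose for tolerability, and Section 10.7.1 lists intolerable symptoms among the reasons for withdrawal.

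For background, Section 5.2.2 reports from pooled phase III data: "discontinuation of perampanel at 4 mg was 2.9%, at 8 mg was 7.7%, and at 12 mg was 19.2" (all percentages). It names dizziness, convulsion and somnolence as the common events behind discontinuation.

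**The concern.** Tolerability asks whether patients can stay on the drug at the intended dose. The protocol's own background describes it partly by discontinuation rates, and says that most treatment-emergent events were mild to moderate. A statistic that starts at Grade 4, apart from suicidality, will miss most of the reasons why a patient would give up an anti-epileptic drug.

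A patient who stops for related Grade 2 dizziness adds nothing to the Section 13.5 percentage. If the stop comes before the end of the treatment period, that patient also leaves the efficacy set. Neither the primary result nor the one statistic in Section 13.5 then shows that the drug could not be continued. Many of these patients have active tumour and may be on chemotherapy (Section 7.1), so an all-cause measure such as days on drug cannot separate intolerance from other reasons for leaving.

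**Working it through.** **1. Denominator.** Section 13.8 requires 61 evaluable patients and enrols 71. A one-sided exact binomial test of 20% against 35% at level 0.1 reproduces the 61: reject at 17 or more responders, exact type I error 0.0879, power 0.9055. Then 61 × 1.16 = 70.8, rounded up to 71. (Dividing by 1 − 0.16 gives 72.6, or 73; the difference does not matter here.) I use n = 71, assuming that every enrolled patient takes at least one dose.

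**2. What each summary shows** for a patient who stops during the treatment period because of a related Grade 1-3 event other than suicidality:

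| Planned summary | Does the stop show? |
|---|---|
| Section 6, any-grade related event | Patient counted, but the same as one with a brief mild event who stayed on drug |
| Section 13.5, unacceptable event | No |
| Section 13.3, days on perampanel | Fewer days, cause unknown |
| Section 13.3, dose modifications by period | Not stated whether a permanent stop counts; no reason; no denominator |
| Sections 7.4 and 13.1, efficacy set | Patient excluded |

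No row gives the number who stopped because of an adverse event.

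**3. Size.** The exact (Clopper-Pearson) 95% limits for x of n are the 0.025 quantile of Beta(x, n − x + 1) and the 0.975 quantile of Beta(x + 1, n − x). For x = 0 the upper limit is 1 − 0.025^(1/71).

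- Rate cited for 8 mg (Section 5.2.2): 71 × 0.077 = 5.5; with x = 5, 5/71 = 7.0% (2.3% to 15.7%).
- Plan's early discontinuation rate, cause not stated (Section 13.8): 71 × 0.16 = 11.4; with x = 11, 11/71 = 15.5% (8.0% to 26.0%).
- Hypothetical higher rate: 14/71 = 19.7% (11.2% to 30.9%).
- Section 13.5 result if every stop in any of these cases was for a related Grade 1-3 event other than suicidality, and no patient had a qualifying event: 0/71 = 0% (0% to 5.1%).

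**4. Why the reason matters.** The interval for 11/71 starts at 8.0%, above 7.7%. If 7.7% counts only adverse-event stops and 16% counts all exits, the trial would appear to exceed the cited rate simply by losing the patients it expects to lose. Without reasons, the two figures cannot be compared.

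**The case against.** The strongest reply is that much of this is already covered. The Section 6 endpoint has no grade limit, so every patient who stops for a related mild or moderate event is counted there. Section 13.3 gives days on drug and the percentage with unplanned dosing in each period, so patients who do not reach the planned dose appear for all causes. Since Section 7.1 names tolerability as the ground for physician dose changes, that table already says something about tolerability. The objective is descriptive, with no test attached, and the safety set includes all treated patients.

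This stands, and it rules out three stronger readings that a reader might infer:

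- **That a drug many patients could not take would be reported as well tolerated, or that the plan cannot address tolerability at all.** The 0/71 result needs Section 13.5 to be read alone. The Section 6 endpoint, if reported, would register these patients.
- **That Section 13.3 leaves out permanent discontinuation, or drops early stoppers from later percentages.** It says neither. Stopping early could well count as unplanned dosing. The defect is silence.
- **That an excess over 7.7% would be a clear tolerability signal.** Section 5.2.2 does not expressly say that these were adverse-event discontinuations, although the surrounding text suggests it. The figure comes from a general partial-seizure population, not glioma, and the plan sets no comparison with it.

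Two practical objections also stand. The medication logs (Sections 7.1.1 and 8.4) record timing and amount, not reasons. And Section 11.1 treats worsening of a pre-existing condition as an adverse event, so a plain count of adverse-event stops would mix seizure worsening with intolerance.

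The reply does not supply the missing number. An any-grade percentage cannot distinguish an event that passed from one that ended treatment, and an all-cause dosing table cannot say why dosing changed.

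**Conclusion.** The point holds in limited form. No planned analysis counts patients who stop perampanel because of an adverse event or links dose limitation to adverse events, and Sections 6 and 13.5 define different endpoints for the same objective. About 5 of 71 patients at the cited 7.7%, or up to 11 of 71 if all of the plan's 16% early discontinuation were due to such events, could stop without adding to the Section 13.5 percentage.

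This rests on four assumptions: all 71 enrolled patients are treated; the list of unacceptable events in Section 13.5 is complete; the stops are for related Grade 1-3 events other than suicidality; and, for the 5 of 71, the 7.7% refers to adverse-event discontinuation. The primary test and the sample size are unaffected. The gap is in how directly the plan answers its secondary objective, and it is worth closing because the change is small.

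**What to change.** 1. Reconcile Section 6 with Section 13.5 by reporting both percentages: patients with any related adverse event of any grade, and patients with an unacceptable event as now defined.
2. Add to Section 13.5, in all treated patients and with exact 95% confidence intervals: (a) the percentage who permanently stop perampanel because of an adverse event before the end of the treatment period, with stops for seizure worsening shown separately; and (b) the percentage who do not reach, or are reduced from, the protocol's planned dose because of an adverse event.
3. In Section 13.3, use all treated patients as the denominator in every dosing period and show those who stopped earlier as their own category.
4. Keep any comparison with the 7.7% in Section 5.2.2 descriptive, and state the assumption that it refers to adverse-event discontinuation.

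The cost is SAP wording, one table, and recording the reason for each stop or dose change on the existing forms, which the documents do not now require. Reported tolerability may look less favourable. No dose, clinical rule, visit or sample size changes.
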